SALTS is a 14-week, two-arm, parallel randomised controlled trial. A two-week baseline period (weeks -2 to -1) will be followed by 12 weeks intervention (weeks 1 to 12) Three hundred and twenty six adults (163 per group) with high BP will be randomised in a 1:1 ratio to receive either the salt reduction intervention (SaltSwitch app + dietary salt substitute) or control (generic information about heart-healthy eating), stratified by ethnicity (Māori and non-Māori) and age (<55yrs and 55yrs+). Randomisation will take place at the end of the baseline phase (beginning of week 1). The primary outcome is 24-hour urinary sodium excretion (mg/day) estimated using a spot (casual) urine sample at week 12. Secondary outcomes are (1) urinary potassium excretion (week 12), (2) average systolic BP (week 12),

Not for Public Circulation or Reproduction

(3) sodium content per 100g of packaged food purchases (week 12), (4) the number of participants achieving BP control (<135/85 mmHg; week 12)[1], and (5) use and acceptability of the SaltSwitch app and dietary salt substitute (week 12). Serious adverse events will be recorded, and if the intervention is effective then cost-effectiveness and cost-utility analyses will also be completed. Both groups will complete home-based BP measures twice per day (morning and evening) in triplicate during weeks -1, 6 and 12; collect a spot (casual) urine sample at weeks -1 and 12; and scan barcodes of all packaged foods purchased for consumption in the home during the 2-week baseline, and during the 2 weeks at the end of intervention (weeks 11 and 12) using a tailored study smartphone application.

Study population and number of participants

Participants will be 326 free-living adults (18yrs+) with high BP who own a smartphone and are willing to do grocery shopping during the study period. A General Practitioner (GP), healthcare provider, or study staff will have confirmed that they have high BP, and \geq 80% will have a recorded systolic BP (SBP) of \geq 140 mmHg at screening. Individuals with high BP and on antihypertensive medication will be eligible since effects of dietary salt reduction are additional to drug therapy[2]. The majority of participants (\geq 70%) will reside in the Auckland region.

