are from a multivariate normal distribution and are missing at random. Sensitivity analyses using different assumptions on the missing data, e.g. complete case analysis and last value carried forward, will also be considered to test the robustness of main trial analysis. Per protocol analysis will be performed for participants with no major protocol violations. Generalised linear regression models will be used to analyse secondary outcomes, using a link function appropriate to the distribution of outcome variable. Like the primary outcome analysis, the regression model will adjust for baseline outcome value and stratification factors where appropriate. Model-adjusted group differences will be presented with 95% confidence intervals and p-values. For the primary and key secondary outcomes, the heterogeneity of treatment effects between Māori and non-Māori participants will be tested using an interaction term between treatment group and ethnicity in the main model, and also for participants in two different age groups (<55yrs and 55yrs+). If the intervention is found to be effective, cost-effectiveness and cost-utility analyses will be pre-specified in a separate economic analysis plan and conducted by an Economist at the University of Otago Wellington.

Not for Public Circulation or Reproduction

2. Study Plan Schematic

Not for Public Circulation or Reproduction

3. Background and rationale

High blood pressure (BP) is the leading cause of premature and preventable death worldwide¹, with the number affected projected to rise from ~0.9 billion in 2000 to ~1.6 billion by 2025². High BP is also a major risk factor for cardiovascular disease (CVD)³, which in turn is responsible for approximately one third of all deaths in countries belonging to the Organization for Economic Cooperation and Development (OECD) ⁴.

The relationship between high BP and dietary sodium intake is widely recognised⁵ with long-term dietary sodium reduction resulting in a fall in BP for both hypertensive and normotensive individuals, regardless of sex, ethnic group⁶⁻⁸ or use of BP lowering medication⁹. While larger reductions in dietary sodium are related to larger falls in BP, even modest reductions can reduce BP and the associated morbidity and mortality from CVD⁸.

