5.5 Randomisation

Eligible participants will be randomised at the beginning of week 1 via a centralised randomisation system. All participants will be randomised in a 1:1 ratio to the intervention or control group, stratified by ethnicity (Māori and non-Māori) and age (<55yrs and 55yrs+) using stratified block randomisation with variable block sizes of two or four.

The RA will activate randomisation for each participant, which will ensure receipt of the correct notifications from the study smartphone app (i.e. intervention or control). The RA will text participants to notify them of the group they have been randomised to and provide the intervention group their SaltSwitch access code. The RA will then call participants in the intervention group to help download and unlock the SaltSwitch app and watch the tutorial. Following the randomisation phone call a study RA will courier a supply of study salt to those in the intervention group.

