6.1 Sample size

A total of 326 participants (163 per group) will provide 80% power at a 5% level of significance (two-sided) to detect a minimum effect size of 0.33 standard deviation (SD) in the primary outcome measure between groups at week 12 allowing for 10% loss to follow-up. This effect size is based on the SD derived from the SaltSwitch pilot study data (1400mg/day) where estimations of 24hr urinary sodium excretion were calculated using spot urine samples and a standard urine volume of 1.99L.

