6.2.2 Treatment effects

The primary outcome will be analysed using linear regression model adjusting for baseline outcome value and stratification factors. Model-adjusted mean differences between two groups will be estimated with 95% confidence interval and p-value. Multiple imputation will be used on missing primary outcome data in the primary intention to treat (ITT) analysis; this method creates multiple imputed datasets for incomplete outcome variables that are analysed using same regression models and combined for one inference. The Markov chain Monte Carlo method will be used to produce the parameter estimates, assuming the data are from a multivariate normal distribution and are missing at random. Sensitivity analyses using different assumptions on the missing data, e.g. complete case analysis and last value carried forward, will also be considered to test the robustness of main trial analysis. Per protocol analysis will be performed for participants with no major protocol violations. Generalised linear regression models will be used to analyse secondary outcomes, using a link function appropriate to the distribution of outcome variable. Similar to the primary outcome analysis, the regression model will adjust for baseline outcome value and stratification factors where appropriate. Model-adjusted group differences will be presented with 95% confidence intervals and p-values. For the primary and key secondary outcomes, the heterogeneity of treatment effects between Māori and non-Māori participants will be tested using an interaction term between treatment group and ethnicity in the main model, and also for participants in two different age groups (<55yrs and 55yrs+).

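### The two sensitivity analyses named in 6.2.2 probe the missing-at-random assumption poorly: complete case repeats it, and last value carried forward is one fixed baseline value

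*Protocol*

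**What the plan says.** Section 6.2.2 fits a linear regression of week-12 urinary sodium on arm, baseline value and stratification factors. Missing outcomes are filled by multiple imputation (MCMC, multivariate normal, MAR). The variables in the imputation model are not listed. On robustness it says: "Sensitivity analyses using different assumptions on the missing data, e.g. complete case analysis and last value carried forward, will also be considered". The Overview repeats this and gives the purpose: these analyses "will also be considered to test the robustness of main trial analysis".

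Four other statements bear on the point:

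- **Timing of the outcome.** The Overview has both groups "collect a spot (casual) urine sample at weeks -1 and 12". In Table 1 (5.21) the only mid-study measure is home blood pressure, so there is no urine sample between baseline and week 12.
- **Baseline sample.** The Overview and 5.20 require one urine sample before randomisation. Section 5.13 instead treats an unreturned baseline sample as missing data.
- **Expected loss.** Section 6.1 sizes the trial "allowing for 10% loss to follow-up".
- **Incentive.** In 5.19 the prize draw for returning the final urine sample is worded for the intervention group only.

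**The concern.** A sensitivity analysis for missing data is useful if it changes the assumption under question, here MAR: that non-returners resemble returners with the same baseline, strata and arm. The protocol describes both named analyses as using different assumptions. One does not, if the imputation uses the ANCOVA covariates. The other takes a different assumption that the two-timepoint design reduces to a single value, and then treats that value as observed.

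This matters here because the trial is open-label, participants return the primary-outcome sample themselves by courier, and the draw rewards return in one arm only. Return could plausibly differ by arm and be related to salt behaviour. Agreement among the three analyses would then be read as robustness, although in some settings they agree because they share an error.

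**Working it through.** **Inputs from the protocol.** Section 6.1 states: "A total of 326 participants (163 per group) will provide 80% power at a 5% level of significance". The same section gives a target difference of 0.33 SD, a two-sided test, a pilot SD of 1400 mg/day and 10% loss; allocation is 1:1 (5.5). The effect is 0.33 × 1400 = 462 mg/day.

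**Inputs assumed.** Baseline to week-12 correlation r of 0.3 to 0.5, the dropout mechanisms, and the loss rates by arm. The protocol gives none of these.

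**1. The plan's own figure.** n per group = 2 × (1.960 + 0.842)² / 0.33² = 144.1, so 145; the t-test version gives 146. Then 146 / 0.9 = 162.2, so 163 per group and 326 in total. The stated size is reproduced.

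**2. Complete case against multiple imputation.** Let b be the complete-case coefficients and X the ANCOVA covariates, with X_o for returners and X_m for non-returners. Imputed outcomes centre on X_m b. Refitting the model to the completed data gives, on average,

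(X'X)⁻¹ (X_o'X_o b + X_m'X_m b) = b.

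The two analyses therefore differ only by Monte Carlo noise when just the week-12 outcome is missing and the imputation uses the same covariates. Simulation (N = 326, 500 trials per scenario, 50 imputations, r = 0.5, true effect -462) agrees:

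| Scenario (missing, intervention/control) | Complete case (SE) | Multiple imputation (SE) | Baseline carried forward (SE) |
|---|---|---|---|
| MAR, 11%/11% | -444 (143) | -444 (143) | -395 (131) |
| Intervention loss depends on outcome, 13%/10% | -583 (141) | -582 (142) | -467 (129) |
| Same, 24%/10% | -677 (146) | -677 (146) | -460 (127) |

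If the imputation adds an auxiliary variable (correlation 0.5 with the outcome) that also drives dropout, the two differ by 25 to 32 mg/day on average.

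**3. Last value carried forward.** The only earlier urine value is week -1, so each missing change is set to zero. With 10% random loss per arm and no drift in control, the estimate is 462 × 0.9 = 416 mg/day, a 10% shrinkage. Under MAR the simulated standard error is 131 against 143, and 131 / 143 = 0.92, about 8% smaller, because filled-in values count as observed.

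**4. Does it expose outcome-dependent loss?** Large-sample limits, true effect -462, logistic dropout on the week-12 value in both arms, non-returners about 900 mg/day higher, r = 0.3 to 0.5:

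| Loss | Complete case | Baseline carried forward | Gap |
|---|---|---|---|
| Control 17%, intervention 6% | -369 to -387 | -378 to -396 | about 9 |
| Intervention 17%, control 6% | -536 to -552 | -421 to -437 | about 115 |

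In the first row both are attenuated (complete case by 75 to 93 mg/day, 16 to 20%; carry-forward by 66 to 84, 14 to 18%) and they agree. In the second, complete case overstates the effect by 74 to 90 mg/day, while carry-forward understates it by 25 to 41.

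**5. What a tipping-point analysis would report.** With 163 × 0.9 = 146.7 evaluable per group, the unadjusted SE = 1400 × √(2 / 146.7) = 163.5, so z = 462 / 163.5 = 2.83. If 10% of intervention outcomes are missing and each is shifted upward by δ, with the SE held fixed, significance is lost when 462 - 0.1δ = 1.96 × 163.5. That gives δ of about 1416 mg/day, roughly one SD. Neither named analysis yields such a figure.

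**The case against.** The strongest reply is that carrying baseline forward is itself a departure from MAR. It makes intervention non-returners worse than comparable returners by roughly the treatment effect, which is close to the scenario most feared: people who did not cut salt do not send the sample. Where high-sodium intervention participants drop out, the route to a false positive, it separates clearly from the imputation (-467 against -582) and lies near the truth. This stands. A reader might infer that the planned set cannot address MAR at all, or that its members will always agree while sharing a bias. The documents do not support either reading: agreement depends on which arm loses more, and where the two agree in step 4 the shared error is toward the null.

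It also stands that the imputation variables are unstated. Auxiliaries such as home blood pressure or scanned purchases, or a missing baseline sample as 5.13 allows, would make complete case and imputation differ. The list is given as examples to be considered, and an analysis plan not seen here may extend it. The absence of further methods is therefore not the complaint. What remains is that the protocol names two methods and describes both as different assumptions: one is not under same-covariate imputation, and the other fits a two-timepoint outcome badly.

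Finally, the loss rates and non-returner gaps are assumed. The intervention-only draw shows that return rates may differ by arm, not that return depends on sodium within an arm. Imputation conditional on arm already handles a plain difference in rates.

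**Conclusion.** The point holds in a limited form. Complete-case ANCOVA is not a different assumption from MAR imputation on baseline, strata and arm. Last value carried forward is baseline carried forward: a single non-MAR scenario that shrinks the effect by about 10% under 10% random loss and carries an SE about 8% smaller than that of multiple imputation. As a check it is unreliable. It diverges by about 115 mg/day when intervention loses more, but agrees within about 10 mg/day with an estimate 16 to 20% too small when control loses more. Those sizes rest on the SD of 1400 and effect of 462 mg/day from 6.1, and on assumed correlations, loss rates and dropout mechanisms.

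It would go too far to say that the plan fails to test MAR where another analysis would succeed: observed data cannot test MAR, and sensitivity analyses only vary it. Nor do the figures show that the trial's conclusion is fragile. At the planned effect with 10% loss, the tipping point is about one SD. The weakness is that the named analyses would not tell the reader this.

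**What to change.** In 6.2.2 and the matching Overview text, replace last value carried forward with delta-adjusted multiple imputation: add a shift to the imputed week-12 values, set separately for each arm, and increase it until the conclusion changes. Report that tipping point. Optionally add one reference-based version in which intervention non-returners are imputed from the control arm. Keep complete case, described as a check on the imputation and not as a different assumption.

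The cost is a couple of sentences, a little extra analysis and some SAS code. No new data are needed, and the primary analysis and sample size are unchanged.

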5.1 Inclusion criteria

Participants will be eligible if they:

- Are aged 18 years or older
- Own a smartphone (iPhone or Android)
- Have a seated SBP of 140-200 mmHg and/or diastolic BP (DBP) of 85-120 mmHg at screening
- Are willing to do grocery shopping during the study period
- Can read and understand English
- Can provide informed consent

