Blood pressure will be collected by the participant on a home-based automated Wi-Fi enable BP monitor using methods adapted from the PATHWAY-2 trial and according to European Society of Cardiology guidelines^{31,32}. Participants will collect BP measures in triplicate after 5 mins rest, 1 minute apart. Measures will be taken both morning and evening, ideally at the same time each day during week -1 +/- two weeks). Participants will receive twice-daily notifications to their phone to remind them to collect their BP. If no BP measures have been received by researchers within one week of the phone call to confirm receipt of the monitor, reminder notifications will be sent and the participant will receive a phone call from a study RA to ensure they are confident in using the monitor. If less than six BP measures have been received within two weeks following courier of the BP monitor, BP data will be considered missing, the participant will be excluded, and the BP monitor will returned to researchers. Blood pressure measures will be received in real time directly from participant's monitors via an Application Programming Interface (API). Consistently elevated SBP (>180mmHg for three consecutive days including any missing days), consistently low SBP (<90mmHg for three consecutive days including any missing days), or major changes in SBP from baseline (>20mmHg) will trigger a notification to be sent to the study staff. The RA will confirm this by investigating the raw data and call the participant advising them that their BP measure is outside the normal range and it is recommended that they visit their GP as soon as possible. The RA will send a letter to notify a participant's GP where required.

Collection of barcodes for packaged food purchases

Participants will scan the barcode of all packaged foods and beverages bought into the home for their consumption during the two-week baseline period (weeks -2 and -1 +/- two weeks). Weekly notifications will be sent to their phone via the study smartphone app to remind them to complete the scanning. Barcodes will be used as unique product identifiers for linking with the Nutritrack supermarket food composition database[30] to determine the sodium content of food purchases. If no shopping purchase information has been returned for the baseline period, these data will be considered missing.

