5.18 Secondary outcome measures

- 1. Urinary potassium excretion (mg per day) at week 12
- 2. Average systolic BP at week 12
- 3. Sodium content (mg per 100g) of packaged food purchases (weeks 11 and 12)
- 4. The number of participants achieving BP control (≤135/85 mmHg; week 12)
- 5. Use and acceptability of the SaltSwitch app and salt substitute at week 12 (intervention group only)

Serious adverse events will also be recorded during the trial period. If the intervention is found to be effective cost-effectiveness and cost-utility analyses will also be conducted.

Not for Public Circulation or Reproduction

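### BP-control model: read literally, section 6.2.2 adjusts for baseline control status (yes/no), although continuous baseline home BP is collected and would be a modestly more efficient covariate

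*Protocol*

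**What the plan says.** Protocol section 5.18 lists two outcomes derived from home BP:

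- Outcome 2: "Average systolic BP at week 12".
- Outcome 4: "The number of participants achieving BP control (≤135/85 mmHg; week 12"), a yes/no result that combines SBP and DBP in one joint cut.

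Section 6.2.2 sets the model for all secondary outcomes: "Generalised linear regression models will be used to analyse secondary outcomes, using a link function appropriate to the distribution of outcome variable". It then sets the covariates: "Similar to the primary outcome analysis, the regression model will adjust for baseline outcome value and stratification factors where appropriate". No separate covariate is named for BP control.

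Section 5.13 describes the baseline readings: "Participants will collect BP measures in triplicate after 5 mins rest, 1 minute apart". They are taken morning and evening in the baseline week. Sections 5.13 and 5.20 require at least six readings before randomisation, so every correctly randomised participant has a baseline mean for both pressures.

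DBP also serves at entry. Section 5.1 reads: "Have a seated SBP of 140-200 mmHg and/or diastolic BP (DBP) of 85-120 mmHg at screening", and section 5.3 applies the same lower limits at referral. DBP on its full scale is not a listed outcome.

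**The concern.** For a continuous outcome such as average SBP, adjusting for the baseline value of the outcome is standard and efficient. Applied literally to a dichotomised outcome, the same rule also dichotomises the covariate. A participant at 136/84 and one at 175/100 are both not controlled at baseline and would carry the same covariate value, although their chances of reaching 135/85 by week 12 differ greatly. The underlying means separate the two and are already in the database.

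What is at stake is precision for one secondary outcome. Randomisation protects the comparison under either covariate, so validity is not in question.

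**Working it through.** **1. The plan's own figure.** Section 6.1 states: "A total of 326 participants (163 per group) will provide 80% power at a 5% level of significance (two-sided"), for 0.33 SD in the primary outcome with 10% loss.

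- Per group: n = 2 × (1.96 + 0.842)² / 0.33² = 144.2, rounded up to 145.
- With 10% loss: 145 / 0.9 = 161.1, rounded up to 162 per group, or 324 in total. The stated 326 agrees within rounding.
- Completers at the stated size: 163 × 0.9 = 146.7, giving 80.7% power.

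This calculation concerns urinary sodium only and does not depend on the present point. It supplies the 147 completers per arm used below.

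**2. Inputs for BP control.**

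- From the protocol: the 135/85 cut, 1:1 allocation, 147 completers per arm and a two-sided 5% level.
- Assumed, because the protocol gives no figures: home BP SD 14 mmHg (SBP) and 9 mmHg (DBP); SBP-DBP correlation 0.6; mean home BP 135/83 or 140/86; baseline to week-12 correlation 0.5, 0.7 or 0.8; a fall of 4/2 mmHg due to treatment.
- Also assumed: a logistic link, since section 6.2.2 leaves the link to the distribution of the outcome.

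**3. Method.** SBP and DBP at baseline and week 12 were simulated as multivariate normal, 1,000 trials per scenario. A participant is controlled if SBP ≤ 135 and DBP ≤ 85. Two models were fitted to the same simulated data:

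- A: logit P(controlled at week 12) = a + b × group + c × (controlled at baseline)
- B: logit P(controlled at week 12) = a + b × group + c × (baseline SBP) + d × (baseline DBP)

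The strata were not simulated. They would enter both models alike.

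**4. Power to detect the treatment effect.**

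| Mean home BP | Correlation | A: yes/no baseline | B: continuous baseline | Gain (points) |
|---|---|---|---|---|
| 135/83 | 0.5 | 52.7% | 54.5% | 1.8 |
| 135/83 | 0.7 | 60.1% | 63.7% | 3.6 |
| 135/83 | 0.8 | 62.5% | 65.9% | 3.4 |
| 140/86 | 0.5 | 47.8% | 50.3% | 2.5 |
| 140/86 | 0.7 | 50.2% | 57.3% | 7.1 |
| 140/86 | 0.8 | 57.0% | 62.1% | 5.1 |

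Each power carries a Monte Carlo standard error of about √(0.5 × 0.5 / 1000) = 1.6 points, so single cells should not be over-read. A separate run of 1,500 trials per scenario at 140/86 gave 54% against 59% (correlation 0.7) and 59% against 66% (0.8), which is the same direction and size.

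**5. Larger effect.** Section 3 cites a meta-analysis with falls of 7.8/4.0 mmHg. At that effect, with correlations of 0.6 to 0.8, power was already at least 97% and the gain was about 1 point or less.

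**6. Type I error.** With no treatment effect (140/86, correlation 0.7), rejection rates were 4.3% for A and 4.9% for B. Both are close to 5%.

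**The case against.** The strongest reply is that section 6.2.2 does not commit to a yes/no covariate. It is one general sentence for all secondary outcomes and ends with a qualifier that leaves latitude. A statistical analysis plan, not shown here, may already name continuous baseline BP. This stands in part: the yes/no covariate is the literal reading, not an explicit commitment. Still, the qualifier reads most naturally as permission to drop an adjuster that does not apply, as for the intervention-only outcome 5. It names no substitute.

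The second reply is that the gain is small, rests on assumed BP inputs, and concerns an outcome for which no power is claimed. At the only BP effect the protocol quotes it nearly vanishes. This also stands and fixes the severity. Section 3 itself rates that evidence as low quality, with few of the studies from high-income countries, so smaller effects remain plausible.

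A reader might infer more than the protocol supports:

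- *That the continuous readings are thrown away.* They are not. SBP is analysed on its full scale as outcome 2, and that test had 80% to 98% power in the same simulations.
- *That DBP has no other role.* It is also an eligibility and referral criterion. What is missing is only a full-scale analysis of DBP as an outcome.
- *That full-scale DBP shows how much power BP control loses.* DBP alone reached 59% to 89% in the simulations, but it is a different outcome answering a different question. Analysing it would not raise power for BP control.
- *That leaving out mean DBP is an error.* The secondary hypotheses in section 4.2 name SBP and BP control, not DBP, so the omission contradicts nothing.

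**Conclusion.** The point holds as a low-severity matter of efficiency. Read literally, section 6.2.2 adjusts BP control for a coarser baseline than the trial collects. Naming continuous baseline SBP and DBP would add roughly 2 to 7 points of power for a 4/2 mmHg fall, and about 1 point or less for a 7.8/4.0 mmHg fall. The means, SDs, correlations, 4/2 effect and logistic link are assumptions, so these figures show direction and rough size only.

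The rule as written causes no bias and no inflation of type I error. The primary analysis and the sample size of 326 are unaffected. The lack of a full-scale DBP outcome is a choice of outcomes, not a defect.

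**What to change.** In section 6.2.2, add one sentence: the BP-control model adjusts for mean baseline home SBP and mean baseline home DBP as continuous covariates, plus the stratification factors, in place of baseline control status. State also that the resulting odds ratio is conditional on baseline BP, so it is not directly comparable with an unadjusted one. If the analysis plan already says this, aligning the protocol wording is enough.

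The cost is that sentence. No new data are needed, and the change should be made before outcome data are seen.

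Optionally, add mean week-12 home DBP as a supportive analysis with the same baseline-adjusted linear model as SBP. Some participants may enter on DBP alone: section 1 expects at least 80% to have screening SBP of 140 mmHg or more, which leaves up to 0.20 × 326 ≈ 65 people. The cost is one more result to report and slightly more multiplicity, which labelling it as supportive contains.
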